Light therapy is a safe, evidence-based, non-pharmacological treatment for MDD and seasonal affective disorder (SAD) with fewer side effects than antidepressants. Light therapy consists of daily exposure to bright light, usually administered at home with a low-cost light device (Lam and Tam, 2009). The antidepressant effect is mediated through the eyes (and not skin exposure), so patients must be awake while using light therapy (Lam and Tam, 2009). The safety and efficacy of light therapy suggest that it would also be effective for maintenance treatment and relapse prevention in SAD or nonseasonal MDD. Unfortunately, however, there are few data on the continued use of light to prevent relapses (Nussbaumer-Streit et al, 2019).

We are planning to conduct a randomized relapse prevention trial to determine if light therapy can be substituted for antidepressants as a maintenance treatment for patients with MDD who are in remission after acute treatment and who wish to discontinue medications. Because there are no previous studies of light therapy for relapse prevention, there are unanswered questions regarding recruitment and feasibility for the study design.

In this feasibility study, we propose an important question: What factors will affect participant adherence to the daily use of light therapy for maintenance treatment? To answer this question, we will conduct a pilot study of open-label treatment with light therapy in a small sample (n=10) of participants meeting eligibility criteria to determine what factors will challenge or enhance adherence to the planned light therapy protocol. The results will provide essential information on recruitment and light therapy to provide guidance for the future randomized study protocol.

Methods

Eligible participants will provide informed consent to join this 12-week open-label trial. Participants will be given standardized verbal and written instructions to use a standard light device at home 5 days a week. After two weeks of light therapy to assess for adverse effects, participants will taper off their antidepressants. Outcome measures will be evaluated at monthly assessments and include validated measures

of depressive symptoms, functional impairment and quality of life. Participants will also remotely complete weekly online assessments.

Setting and Recruitment

Participants will be recruited from the Mood Disorder Centre and by advertisement. Some study visits (e.g., baseline, study termination, and relapse assessment visits) will be conducted at the Mood Disorder Centre outpatient clinic in the Djavad Mowafaghian Centre for Brain Health, but most assessment visits will be virtual (i.e., via Zoom and online surveys).

Participants

Ten participants will be recruited who meet the following eligibility criteria: [1] Outpatients 19 to 65 years of age; [2] DSM-5 criteria for MDD past or recurrent episode as determined by the Mini International Neuropsychiatric Interview; [3] taking an antidepressant for no more than six months; [4] participant desire to discontinue antidepressant treatment because of adverse effects or other reasons; [5] total score ≤ 10 on the clinician-rated Montgomery-Asberg Depression Rating Scale [MADRS]; [6] Willing and able to complete self-report and online assessments including sufficient fluency in English.

Exclusion criteria: [1] Any psychiatric diagnosis other than MDD that is considered the primary diagnosis, including Bipolar I or Bipolar-II (lifetime); [2] MDD with psychotic features (lifetime); [3] significant personality disorder diagnosis [e.g., borderline, antisocial]; [4] High suicidal risk, defined by clinician judgment; [5] History of drug or alcohol abuse, with a severity of at least moderate or severe within 6 months before screening; [6] Significant neurological disorders, head trauma, or other unstable medical conditions; [7] regular use of psychotropic medication other than an antidepressant or benzodiazepines (e.g., antipsychotics, mood stabilizers); [8] history of severe withdrawal effects with antidepressant discontinuation; [9] retinal disease or other eye condition preventing use of bright light therapy; [10] use of photosensitizing medication within 1 week of baseline visit.

Treatment

Light Therapy: The active treatment consists of daily exposure to a standard light device (e.g., fluorescent light box such as the Carex Day-Light Classic, emitting 4000 Kelvin white light rated at 10,000 lux at 14 inches from screen to cornea, with an ultraviolet filter) for 30 minutes as soon as possible after awakening, preferably between 7:00-8:00 am. Patients will be given standardized verbal and written instructions to use the light device at home 5 days a week (Monday to Friday) for the 12 weeks of the study. Adherence will be monitored using daily logs of device treatment times completed by patients.

Antidepressant Tapering: After using light therapy for 2 weeks (to assess potential adverse effects), participants will taper off antidepressants according to a standardized clinical algorithm, which addresses potential discontinuation effects. We are experienced with discontinuing antidepressants with patients, although we anticipate that any discontinuation symptoms will be mild and transient since participants in this study will have taken antidepressants for less than 6 months. Participants will be assessed every 2 weeks until antidepressants are stopped, and thereafter every 4 weeks till the end of the study.

Outcome Assessments

Clinician assessments to be completed at baseline (Week 0), Week 4, Week 8, Week 12, and/or study termination visits:

- 1) Montgomery Asberg Depression Rating Scale (MADRS)
- 2) Clinical Global Impression – Severity (CGI-S)
- 3) Concomitant medications
- 4) Adverse Events
- 5) Toronto Side Effects Scale (SES)
- 6) Discontinuation Emergent Symptoms and Signs (DESS) scale

Participant self-report measures to be completed during baseline (Week 0), Week 4, Week 8, Week 12, and/or study termination visits (through a REDCap interface):

- 1) Quick Inventory of Depressive Symptomatology-Self-Report (QIDS-SR)
- 2) Generalized Anxiety Disorder 7-item (GAD-7);
- 3) British Columbia Cognitive Complaints Inventory (BC-CCI);
- 4) Pittsburgh Sleep Quality Index (PSQI);
- 5) Sheehan Disability Scale (SDS);
- 6) Frequency, Intensity, and Burden of Side Effects Rating (FIBSER);
- 7) Adverse Events Scale, Self-Rated;
- 8) Lam Employment Absence and Productivity Scale (LEAPS);
- 9) Quality of Life Enjoyment and Satisfaction Questionnaire (Q-LES-Q);
- 10) World Health Organization Quality of Life Short Version (WHOQOL-BREF);
- 11) EuroQol Group; 5 dimension; 5 level (EQ-5D-5L);
- 12) Healthcare Economic Assessment (HEA).

Participant measures to be completed at study termination visit (end of study at Week 12 visit, early termination, or the relapse assessment/verification visit).

- 1) CNS-VS computerized cognitive assessment (also at baseline);
- 2) Exit questionnaire regarding adherence factors for light therapy;
- 3) Semi-structured qualitative interview focused on issues of adherence.

Summary of Visits

Week -1	Week 0	Week 2	Week 4	Week 8	Week 12	Any time	Week +1
Zoom	At clinic	Zoom	Zoom	Zoom	At clinic	At clinic	At clinic
Screening	Baseline				Study end	Relapse assessment visit	Relapse verification visit
	Start light therapy	Start medication taper	Stop medication		End light therapy		

Assessment of Relapse

Participants will complete the PHQ-9 self-rated depression rating scale each week online. If the weekly PHQ-9 total score is ≥ 10 , a relapse-assessment visit will be scheduled as soon as possible to determine if patient meets criteria for relapse.

Relapse will be defined as any of the following: [1] MADRS total score ≥ 22 for at least 2 consecutive weeks. If the relapse criterion of MADRS total score ≥ 22 is met at a scheduled assessment visit or an unscheduled relapse-assessment visit, an additional visit (i.e., the relapse-verification visit) will be scheduled within 1 to 2 weeks to verify the relapse; [2] Hospitalization for worsening of depression; [3] Suicidal ideation with intent, or suicidal behavior; [4] Any change in treatment (e.g., starting an antidepressant).

Subjects who relapse but do not require a Relapse Verification Visit (i.e., they meet relapse criteria other than that based on the MADRS total score) will complete the First Symptom of Relapse -- Self Assessment (FSR-SA). Any relapse event will be communicated by the study physician to the subject's treating physician.

Outcome Measures and Analysis

The primary feasibility outcome will be [1] rate of adherence ($>75\%$ of total daily sessions) to light therapy during the 12-week follow up. Secondary feasibility outcomes include patient factors that may challenge or enhance adherence, obtained via the exit questionnaire and qualitative interviews conducted at the end of the study. Secondary clinical outcomes include changes in MADRS and other outcome measures from baseline to end of treatment. Descriptive and appropriate statistical tests will be used for the analysis.

Qualitative/mixed methods: Semi-structured interview questions will be developed with specific exploratory interview probes created for participants showing higher or lower levels of adherence (determined on the basis of the quantitative data), as appropriate. All interviews will be digitally recorded,

transcribed verbatim, and a coding framework developed. Interpretative description, a qualitative methodology developed to generate knowledge relevant for the clinical application will be applied as the analytic framework. As is standard in qualitative methodology, data analysis will begin with the delivery of the first interview and proceed concurrently; summaries of the main factors relating to adherence or non-adherence will be created, and an interpretive account constructed.

Given our mixed methods approach, a sample of 10 participants will allow us to determine whether patients are likely to adhere to light therapy for 5 days a week over a longer term duration. The 12-week follow up duration for the pilot study, although shorter than the 12-month follow up planned for the proposed randomized trial, balances the pragmatic need to complete the pilot before the planned date for submitting the randomized study grant.

Potential Benefits and Potential Risks

As in all studies occurring in a clinical environment, the risk-benefits analysis must be carefully considered. The risks to the subjects identified in the study include: the risk of adverse or serious adverse reactions to the light therapy; the risk of discontinuation/withdrawal symptoms from antidepressant tapering; the risk of depressive relapse if the light therapy is not effective as maintenance treatment; the risk that the evaluations and questionnaires used in this study may make subjects feel uncomfortable or upset.

If a participant experiences a depressive relapse, the study doctor may advise the participant's family physician and/or regular psychiatrist in re-evaluating the current treatment being received. A participant experiencing acute distress (with immediate risk of self-harm) will be assisted by the study team following a standard operating procedure that could include developing a safety plan, and/or arranging for hospitalization or other medical care, among other actions.

Tests/questionnaires might provoke mild psychological distress in subjects, who can decline to provide answers if they do not feel comfortable responding. Psychological/cognitive testing might also be anxiety-provoking for subjects owing to concerns about performance and possible errors. However, no negative effects are expected to persist beyond the visits when subjects are completing testing for this study.

Potential benefits to the subjects include careful medical monitoring, and safely discontinuing antidepressants. However, no benefits from this study can be guaranteed.

Risk Management

We have standard operating procedures in place to ensure safety of participants. Participants showing clinical worsening or emergence of suicidal ideation during the trial will be withdrawn from the study and treated with standard clinical care.

If needed, clinical visits (via Zoom or at clinic) can be arranged at any time during the study period. At the end of the study, participants will be provided with psychiatrist recommendations for further care. Participants may continue with light therapy by purchasing a light device (retail cost \$150-\$300).

Confidentiality and Data Security

Ethical approval for the study will be obtained from the UBC Clinical Research Ethics Board. Participants will provide informed consent.

Research Electronic Data Capture (REDCap) is a web-based system for data collection where participants will complete the self-report questionnaires and enter data in a web browser from remote locations. REDCap includes a complete suite of features to support Health Insurance Portability and Accountability Act (HIPAA) compliance, including a full audit trail, user-based privileges, and integration with the institutional server.

The virtual visits are conducted via UBC Zoom, which has been approved by Vancouver Coastal Health for both privacy and security. Participants will receive the standard Zoom disclosure and information form as approved by Vancouver Coastal Health.

References

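### Baseline-to-end change, the only summary named for the clinical scales, can be near zero for DESS even if discontinuation symptoms occurred, and the Week 4 and Week 8 DESS ratings enter no named result

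*Combined protocol and SAP*

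**What the plan says.** All references are to the combined protocol and SAP.

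- **Outcome Measures and Analysis** gives the clinical summary: "Secondary clinical outcomes include changes in MADRS and other outcome measures from baseline to end of treatment". The only other general analysis statement there is: "Descriptive and appropriate statistical tests will be used for the analysis". No by-visit summary, highest score or count of affected participants is named for any scale.
- **Outcome Assessments** sets the timing: "Clinician assessments to be completed at baseline (Week 0), Week 4, Week 8, Week 12, and/or study termination visits". The sixth item in that list is the "Discontinuation Emergent Symptoms and Signs (DESS) scale".
- **Treatment** (antidepressant tapering) states the expected course: "we anticipate that any discontinuation symptoms will be mild and transient". Tapering begins after two weeks of light therapy.
- **Summary of Visits** puts the start of the taper at Week 2, the medication stop at Week 4 and the end of light therapy at Week 12.
- **Potential Benefits and Potential Risks** lists withdrawal symptoms from the taper among the risks to participants.

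**The concern.** DESS is there to detect symptoms that arise as the antidepressant is withdrawn. A two-point change score measures what remains at the second point. Here the first point comes before the taper and the second comes well after the planned stop. If symptoms behave as the protocol expects, they are absent at the first point and gone by the second, so a near-zero change would not tell a participant who had symptoms from one who had none.

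What is at stake is the usefulness of the DESS data. The pilot is meant to guide a randomized trial in which light therapy replaces antidepressants. A mean DESS change near zero could be read as evidence that stopping caused no symptoms, when the ratings closest to the stop were not part of the summary.

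**Working it through.** The plan gives no figure to reproduce: the sample of 10 is not derived from an error rate, power or effect size. The check sets the schedule against the named summary and then illustrates the size.

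**1. Ratings used and unused** (Outcome Assessments; 10 completers).
- Collected: 10 × 4 = 40. Post-baseline: 10 × 3 = 30.
- Used by a Week 0 to Week 12 change: 10 × 2 = 20.
- Unused: 10 × 2 = 20 (Weeks 4 and 8), that is, 20 of 30 post-baseline ratings.

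**2. Distance from the stop to the last rating.** Tabulated stop at Week 4: 12 − 4 = 8 weeks. If the taper runs longer: 12 − 6 = 6 weeks for a Week 6 stop, 12 − 8 = 4 weeks for a Week 8 stop.

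**3. Size of the change for a fading symptom excess.** Assumed, not from the documents: Week 0 excess 0, a 5-point peak at the Week 4 stop, and exponential decay with half-life h. The excess at week t is 5 × 0.5^((t − 4)/h).

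| h (weeks) | Week 4 | Week 8 | Week 12 = change from Week 0 |
|---|---|---|---|
| 0.5 | 5.0 | 0.02 | 0.00 |
| 1 | 5.0 | 0.31 | 0.02 |
| 2 | 5.0 | 1.25 | 0.31 |
| 4 | 5.0 | 2.5 | 1.25 |

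The change is 0.31 points or less for half-lives up to 2 weeks. It is no longer near zero when symptoms persist. Placing the peak on the Week 4 visit is the most favourable case for by-visit reporting, so step 4 relaxes it.

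**4. Share of episodes that any rating would catch.** Assumed: onset o is uniform from Week 2 to one week after the stop, duration d is fixed, and a rating at week w looks back r weeks. An episode is caught at w if o ≤ w and o + d ≥ w − r. The documents give no look-back period, so r = 0/1/2 weeks is shown in that order.

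Example (stop Week 4, d = 2, r = 0): o lies in [2, 5]. Week 4 catches o from 2 to 4, which is 2/3. Week 8 needs o ≥ 6 and Week 12 needs o ≥ 10, so neither adds anything. All ratings catch 67%; Week 12 alone catches 0%.

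Week 4 stop, percent caught:

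| d (weeks) | Week 12 alone | Any of Weeks 4, 8, 12 | Any rating, onset only in Weeks 4 to 5 |
|---|---|---|---|
| 1 | 0/0/0 | 33/67/67 | 0/0/0 |
| 2 | 0/0/0 | 67/67/100 | 0/0/100 |
| 3 | 0/0/0 | 67/100/100 | 0/100/100 |
| 4 | 0/0/0 | 100/100/100 | 100/100/100 |
| 6 | 0/0/33 | 100/100/100 | 100/100/100 |

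Week 8 stop, percent caught:

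| d (weeks) | Week 12 alone | Any of Weeks 4, 8, 12 |
|---|---|---|
| 1 | 0/0/0 | 29/57/71 |
| 2 | 0/0/14 | 57/71/100 |
| 3 | 0/14/29 | 71/100/100 |
| 4 | 14/29/43 | 100/100/100 |
| 6 | 43/57/71 | 100/100/100 |

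That three ratings catch at least as much as one of them is automatic and proves nothing. The tables are useful for the size of the gap, and that size depends on the assumptions. The last column of the first table shows the limit: brief symptoms arising just after the stop can fall between visits whatever summary is used.

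**5. Chance in a worst-score count.** If a participant's four scores differ only by noise, without ties, the chance that the highest of three later scores exceeds Week 0 is 3/4, or 7.5 of 10 participants. At any single visit it is 1/2, or 5 of 10. A count of anyone with a new or worsened symptom at any visit works item by item and would be inflated further.

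**The case against.** The strongest reply is that the plan does not exclude by-visit reporting. The summary sentence is worded as a non-exhaustive list, descriptive analysis is allowed, and Methods says "Outcome measures will be evaluated at monthly assessments and include validated measures" "of depressive symptoms, functional impairment and quality of life". One could read the change over the treatment period as taking in the monthly values, and tables by visit for ten people would need no amendment. This stands in part. A reader might infer that the plan rules out by-visit DESS results; it does not. But it does not name them either, and the ordinary reading of the one named summary is a two-point contrast. The Methods description also leaves harm scales unmentioned, so on a narrower reading DESS has no named summary at all.

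A reader might extend the point to the Toronto Side Effects Scale (SES) and the side-effect burden rating (FIBSER). The documents do not support that. The expectation of short-lived symptoms concerns discontinuation only. Week 0 for those scales is rated on the antidepressant, and some participants enter because of its adverse effects. For them an on-drug to off-drug change is meaningful and may show improvement.

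A reader might also infer that all interim ratings go unused. MADRS is a clear exception, because its interim values count towards relapse when the threshold "is met at a scheduled assessment visit or an unscheduled relapse-assessment visit".

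Nor is participant safety at issue. Tapering follows a clinical algorithm, adverse events are recorded at the same visits (though no tabulation is named for them), and Risk Management allows extra clinical visits at any time.

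**Conclusion.** The point holds for DESS and is minor. For a completer on the tabulated schedule, baseline-to-end change compares a rating before the taper with one 8 weeks after the stop. It can therefore be near zero when symptoms came and went, and 20 of 30 post-baseline ratings enter no named result.

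The conclusion rests on reading the summary sentence together with the Outcome Assessments list, on the Week 2 and Week 4 taper dates, and on the protocol's own expectation about duration. It weakens with a longer taper (4 weeks from a Week 8 stop to the last rating), with persistent symptoms, and for participants who leave early, whose final rating may fall near the taper. The point scores and percentages are illustrations under stated assumptions, not estimates for this trial.

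The primary outcome is adherence and the plan claims no conclusion about the safety of discontinuation, so neither is affected.

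**What to change.** Add to Outcome Measures and Analysis:

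- DESS will be listed by participant and visit, with time since the last antidepressant dose.
- DESS will be summarised by visit and by each participant's highest score after taper start.
- Any count of participants with a new or worsened symptom at any visit will be shown only beside the counts at each visit.

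Keep baseline-to-end change for MADRS, function, quality of life, SES and FIBSER. By-visit values for SES and FIBSER are optional; if given, they should show participants who improved as well as those who worsened.

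The cost is two or three sentences and a 40-row listing, with no new visits, data or staff. There are downsides. The harm figures will look less favourable, and no control arm exists to interpret them. Highest scores and any-visit counts are inflated by chance (7.5 against 5 of 10 in the noise-only case above). Brief symptoms between Weeks 4 and 8 may still be missed, because the limit there is the visit schedule and not the summary.
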